# AE and SAE Assessment Guidelines Specific to the LIPP Study

*Key Criteria:* to determine if the event is unexpected, related to participation in the research study and involves risk to human subjects or others.

If an adverse event meets the criterion of unexpected, related or possibly related, and poses risk of harm to other subjects, the study coordinator will notify one of the Multiple Principal Investigators, [name] or [name], within 24- hours who will then inform the DSMB Chair and the Tufts Health Sciences IRB; the reviewing IRB of record.

To evaluate AEs and SAEs, a licensed medical professional will apply the following assessment criteria:

#### **Event Expectedness**

#### Unexpected Medical Events:

These are the medical events that are not described in the current IRB-approved protocol or informed consent, taking into account the characteristics of the participant population being studied (e.g. pregnant population). *Expected medical events*\*:

### PROTOCOL TITLE: Lifestyle Intervention in Preparation for Pregnancy (LIPP) VERSION DATE: March 31st, 2023

- Symptoms and risk related to normal pregnancy progression such as nausea, vomiting, fatigue, urinary frequency, increased or decreased appetite, transient dizziness, mild back or breast pain or discomfort, mild mood changes, miscarriage, preterm delivery, still birth, low birth weight, problems with placenta and birth defects,
- Symptoms related to fasting for at least 8-hours and related hypoglycemia: headache, nausea, and lightheadedness
- Symptoms related to hypoglycemia such as fainting, fast heart rate, sweating, shakiness, difficulty paying attention, sudden moodiness or irritability, unconscious
- Symptoms related to venous blood draw such as bruising, bleeding, swelling, and pain, fainting, lightheadedness and infection at the injection site.
- Symptoms related to consuming the glucose solution for the diabetes testing such as brief nausea, vomiting, tiredness, lightheadedness and upset stomach.

\* While the above medical events may be expected, they will be collected for outcome purposes.

# Event Severity using Common Terminology Criteria for Adverse Events (CTCAE)

Grade refers to the severity of the AE. The CTCAE displays Grades 1 through 5 with unique clinical descriptions of severity for each AE based on these general guidelines:

- Grade 1 Mild; asymptomatic or mild symptoms; clinical or diagnostic observations only; intervention not indicated.
- Grade 2 Moderate; minimal, local or noninvasive intervention indicated limiting age-appropriate instrumental activities of daily living.
- Grade 3 Severe or medically significant but not immediately life-threatening; hospitalization or prolongation of hospitalization indicated; disabling; limiting self-care.
- Grade 4 Life-threatening consequences; urgent intervention indicated.
- Grade 5 Death related to AE.

#### Event Relatedness

Related: The incident, experience, or outcome is more likely than not caused by study procedures.

- A reasonable time course would be within the 1-4 hours the subject is receiving oral glucose tolerance testing.
- Symptoms abate once the study product is discontinued and patient has received a snack or drink. Symptoms are not explained by other factors such as concomitant medications or current illness

*Possibly Related:* There is reasonable possibility that the incident, experience or outcome may have been caused by study procedures.

• A reasonable time course would be within 24-48 hours the subject either fasting for the study or receiving the oral glucose tolerance testing.

or

• Symptoms may be explained by other factors such as concomitant medications or current illness

Adverse Event	
VO 2 max	Falling off treadmill
VO 2 max	Exhaustion
VO 2 max	Feeling like heart is pounding very fast very hard

VO 2 max	Dizziness
VO 2 max	Heart rhythm abnormalities
VO 2 max	Chest pain
VO 2 max	When the mask is on the face, this might feel uncomfortable
Structured exercise	Feeling like heart is pounding very fast or very hard
Structured exercise	Dizziness
Structured exercise	Heart rhythm abnormalities
Structured exercise	Chest pain
Laboratory studies	Bruising at IV site
OGTT	Nausea from glucose load
OGTT	Bruising from IV site
Resting Metabolic	
Rate	Claustrophobia
Bod Pod	Claustrophobia
Neonatal	
Anthropometrics	Bruising from skinfold calipers
Maternal	
anthropometrics	Bruising from skinfold calipers

#### Serious Adverse Event

VO 2 max	Heart attack
VO 2 max	Death
Structured exercise	Heart attack
Structured exercise	Death

#### 7.2 Reporting Procedures

- Describe the protocol-specific reporting procedures, including who will be responsible for each step (e.g., PI, Data Coordinating Center, Medical Monitor), which forms should be completed, timeframes for reporting, how reports will be distributed, and what follow-up is required.
- Include specific details of reporting procedures for:
  - Deaths, life-threatening events, pregnancies PI
  - Other SAEs PI or study coordinator
  - Other AEs study coordinator
  - Other UPs study coordinator All the details are noted in the DSMB charter. The reporting mechanisms are noted above, since different adverse events are reported based on the degree of severity
- Ensure that the reporting procedures meet the reporting requirements of the FDA, NIH, OHRP, sponsor, study leadership and any other regulatory body that applies to the study, as applicable. NIH will receive a yearly non-competitive renewal notice of the progress of the study and any serious adverse events related to the study protocol.

## 7.3 Reportable New Information

 Indicate also, that reportable new information will be reported to the IRB per the Tufts Health Sciences IRB's Reportable New Information policy. If your reporting plan to the IRB differs from the IRB's policies, please describe it in detail. NA Reportable new information will be reported to the IRB per the Tufts Health Sciences IRB's Reportable New Information Policy

# 8 Statistical Considerations

# 8.1 Study Endpoints

- Describe the primary and secondary study endpoints.
  - The primary outcome measure of this proposal is lower neonatal adiposity at birth in the LIPP group relative to: 1) the usual care/control group. As secondary outcomes we anticipate that prior to a subsequent pregnancy, LIPP will produce significant improvement (absolute and percent changes) in maternal weight and body composition, and more importantly improved insulin sensitivity,  $\beta$ -cell function, incretin response to glucose, lipid and inflammatory biomarkers, compared to the Control group. We also expect reduced insulin resistance, umbilical cord lipids and inflammatory profiles in babies born to LIPP subjects compared to Controls.
- Describe any primary or secondary safety endpoints. The risk of having a small for gestational age baby or preterm delivery will be followed closely in the intervention group, as this is a theoretical risk.

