- There are no risks to the fetus or embryo for healthy eating and exercise during pregnancy as these are the current recommendations of the ACOG. If a woman becomes severely dehydrated, this could decrease blood flow and oxygen to the fetus. This situation is often accompanied by symptoms as noted above in the mother. Care will be taken to avoid these conditions because of the presence of certified trainers in the intervention group.
- If applicable, describe risks to people other than the participating subject, e.g., risks to family members, friends, others or risks to the community. NA There may be benefit to the family because of women most commonly doing the greatest share of meal planning for the family.
- If applicable, describe risks to study investigators or staff performing the study procedures due to research with high risk populations (e.g. prisoners, intravenous drug users, patients with major psychiatric issues, etc.). NA

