# 🗹 Yes 🛛 No

If Yes, describe the following:

• Any preclinical studies, including studies on pregnant animals, and clinical studies, including studies on non-pregnant women, that have been conducted that provide data for assessing potential risks to pregnant women and fetuses.

The preliminary data that was obtained in Cleveland was data that included the number of women who might be eligible based on inclusion and exclusion criteria. The other preliminary data was the review of the average time to the second pregnancy. None of these information provided data related to risk to subjects relative to intervention.

• Whether the risk to the fetus is caused solely by interventions or procedures that hold out the prospect of direct benefit for the woman or the fetus or if there is no prospect of benefit to the fetus, the risk to the fetus is NOT greater than Minimal Risk, and the purpose of the research is the development of important biomedical knowledge which cannot be obtained by any other means.

There is no risk to the fetus from participation in the study. The ACOG recommends that pregnant women partake in physical activity during pregnancy for 30 min at least 5 days a week. Our study protocol recommends that all subjects follow ACOG guidelines for diet and physical activity and gain weight according to IOM recommendations from 2009.

• The biomedical knowledge that is expected to result from this research for this population. Importance of the Knowledge Gained

The importance of the knowledge to be gained by this proposal is the ability to determine if Lifestyle Interventions in Preparation for Pregnancy can achieve concrete (real) results in the efforts to stem the epidemic of obesity in women and their offspring. This study will also provide information as to the mechanisms of why lifestyle intervention before rather than only during pregnancy results in improved outcomes. Although the concept of pre-pregnancy lifestyle intervention has been recognized previously as potentially worthwhile, there have been few if any studies employing such a study design, because of the perceived difficulty in recruiting women prior to pregnancy. Based on our history of conducting research studies in women before during and after pregnancy, a study design of recruiting obese women immediately after pregnancy and incorporating the community into the lifestyle interventions, we believe that this approach will have applicability in many other populations.

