#### Serious Adverse Events (SAEs)

Serious Adverse Events (SAEs) or "Unanticipated Problems Involving Risk to Subjects or Others," are characterized as symptoms which are harmful to the subject and result in significant outcomes which are reportable to the respective IRBs and the study's DSMB.

[figure not shown]
Examples of serious adverse events are:

- Death
- Life threatening medical events that place a subject at immediate risk of death from the event as it occurred
- Results in impatient hospitalization or prolongation of existing hospitalization
- Results in persistent or significant disability or incapacity as a result of the study intervention
- Events that, based upon appropriate medical judgment, may jeopardize the subject's health and may require medical or surgical intervention to prevent one of the other outcomes listed in this definition.

The flow chart below provides an algorithm for determining whether an adverse event meets the definition of an "unanticipated problem involving risk to subjects or others."

PROTOCOL TITLE: Lifestyle Intervention in Preparation for Pregnancy (LIPP) VERSION DATE: March 31st, 2023

Adverse Events which follow the above figure, that meet the criteria of unexpected, fatal or lifethreatening, and related or possibly related to the research intervention must be reported to the IRB and the DSMB within 24 hours of learning of the event. If necessary, a subsequent follow-up report with the details of the event will be submitted as well. All other reportable adverse events will be submitted to the IRB within 10 working days of the investigator learning of the event. Reportable events will be submitted through the respective IRB's system.

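### The two named safety endpoints, small for gestational age and preterm delivery, are tied to the intervention arm only; report them by arm, and tidy the stillbirth and fetal-risk wording

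*Combined protocol and SAP*

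**What the plan says.** **Safety endpoints.** Section 8.1 answers the safety-endpoint prompt in one sentence: "The risk of having a small for gestational age baby or preterm delivery will be followed closely in the intervention group". It gives the reason that the risk is theoretical. The efficacy outcomes in the same section are all stated relative to control.

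**Analysis.** Section 8.2 compares neonatal fat mass, birth weight and cord cytokines between arms. It does not mention SGA, preterm delivery or stillbirth as outcomes. Section 6.6 leaves the choice of safety tests to the study statistician and refers to a DSMB charter.

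**Data.** Sections 4.4.2 and 5.1 describe collection of delivery and infant data without restriction by arm. The reduced-funding schedule in 5.1 lists neonatal measurements under a block headed for both groups.

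**Event reporting (7.1).** The list of expected events includes "miscarriage, preterm delivery, still birth, low birth weight, problems with placenta and birth defects". A footnote adds: "While the above medical events may be expected, they will be collected for outcome purposes". One 24-hour route is for events "that meet the criteria of unexpected, fatal or lifethreatening, and related or possibly related to the research intervention". The LIPP-specific route begins: "If an adverse event meets the criterion of unexpected, related or possibly related, and poses risk of harm to other subjects".

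**Fetal risk.** Section 6.10 states: "There is no risk to the fetus from participation in the study". Section 2.2 opens in the same sense, "There are no risks to the fetus or embryo for healthy eating and exercise during pregnancy", and shortly afterwards adds: "If a woman becomes severely dehydrated, this could decrease blood flow and oxygen to the fetus".

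**The concern.** Sub-Aim 1b in section 3 expects lower birth weight in the LIPP arm. If the whole distribution shifts down, some increase in SGA is the natural adverse counterpart of the intended effect, which is presumably why 8.1 names it. The safety question is therefore whether SGA and preterm delivery are more frequent than in controls. A count from the LIPP arm alone cannot answer that without an external rate, and the documents give none. The randomised control arm is the right reference, and its data are collected anyway.

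Two lesser matters belong with this:

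- Stillbirth is listed as expected, so it fails one of the conditions for 24-hour reporting. Outside that rule no time limit for telling the DSMB is stated.
- The unqualified fetal-risk statement in 6.10 cannot stand beside the theoretical risk in 8.1.

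**Working it through.** **1. Births available: the plan's own figure.** Section 8.2 assumes 50% dropout, so 200/2 × (1 − 0.5) = 50 births per arm. Its power statements reproduce with power = Φ(δ/(SD·√(2/n)) − 1.96), two-sided 0.05 assumed:

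- Fat mass, SD 225 g: standard error 225 × √(2/50) = 45.0 g. For 146 g, 146/45 = 3.244, giving 90.1%. For 126 g, 126/45 = 2.80, giving 80.0%. The noncentral t gives 89.5% and 79.2%.
- Birth weight, SD 700 g: standard error 140 g. For 455 g the power is 90.1%, and for 393 g it is 80.2%.

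The stated figures hold. No rate, sample size or power is stated for SGA, preterm delivery or stillbirth.

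**2. What a LIPP-only count can show.** Suppose 7 of 50 LIPP births are affected: 14%, exact 95% CI 5.8% to 26.7%. The background rate is an assumption, so a range is used. P(X ≥ 7) for a binomial with n = 50:

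| Assumed background | P(7 or more) |
|---|---|
| 5% | 1.2% |
| 10% | 23.0% |
| 15% | 63.9% |

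The same count runs from alarming to unremarkable depending on a rate that the documents do not supply.

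**3. What the control arm adds.** Newcombe interval for the difference, same 7/50 in LIPP:

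- Controls 2/50: the Wilson limits are 7.0% to 26.2% for LIPP and 1.1% to 13.5% for controls. Lower limit: 0.10 − √[(0.140 − 0.0695)² + (0.1346 − 0.040)²] = −0.018. Upper limit: 0.10 + √[(0.2619 − 0.140)² + (0.040 − 0.0110)²] = 0.225. The difference is +10.0 points (−1.8 to 22.5).
- Controls 7/50: 0.0 points (−14.1 to 14.1).

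The two readings differ, but both intervals are wide and include zero.

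**4. Power of that comparison.** Pooled z-test, two-sided 0.05, 50 per arm: power = Φ[(d − 1.96·SE₀)/SE₁].

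- 5% against 10%: SE₀ = √(2 × 0.075 × 0.925/50) = 0.0527 and SE₁ = √[(0.05 × 0.95 + 0.10 × 0.90)/50] = 0.0524. (0.05 − 0.1032)/0.0524 = −1.015, giving about 15%.
- 10% against 20%: SE₀ = 0.0714 and SE₁ = 0.0707. (0.10 − 0.1400)/0.0707 = −0.565, giving about 29%.

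Eighty per cent power for these doublings would need 435 and 199 births per arm. The by-arm table is estimation for monitoring, not a test.

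**5. Stillbirth reporting, text against text (7.1).**

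- General 24-hour route: the event must be unexpected, fatal or life-threatening, and at least possibly related.
- LIPP-specific route: it must be unexpected, at least possibly related, and carry a risk of harm to other subjects.
- Stillbirth is on the expected list, so as listed it fails the first condition of both.
- Relatedness is a separate barrier. Section 7.1 opens by reporting events if causal, and its relatedness time windows are tied to fasting and the OGTT (at most 48 hours). A delayed effect of weight loss before conception would rarely fit.
- Serious events are reportable to the IRBs and the DSMB, but the 10-working-day limit runs to the IRB. No DSMB limit is stated outside the 24-hour rule.

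**6. Fetal risk, text against text.** The statement in 6.10 conflicts with the theoretical SGA and preterm risk in 8.1. It agrees with the opening sentence in 2.2 but omits the dehydration caveat that follows there.

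**The case against.** **The charter may already cover this.** Section 6.6 says the DSMB reviews safety and efficacy data, leaves the tests to the statistician, and refers to a charter and to open and closed reports. A reader might infer from 8.1 that control-arm safety data are not gathered or will never be compared. The documents do not support that: 8.1 does not say only, the data are collected in both arms, and the charter is not available to check. What stands is that the protocol text states a one-arm rule and requires no comparison.

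**The comparison is weak.** It is. At 15% to 29% power for a doubling it will not settle the question. It does replace an uninterpretable number with an estimate and an interval.

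**The expected list is not the decisive gate.** A reader might infer that it alone keeps stillbirth and preterm delivery off the 24-hour route, or that the DSMB could wait a year to hear of a stillbirth. Neither follows. Severity, relatedness or risk to others are also required, and 7.1 allows severity or frequency to make an event unexpected. Serious events are reportable to the DSMB, other reportable events reach the IRB within 10 working days, and the yearly meeting in 6.6 is a minimum. One flow chart in 7.1 is also not shown. The narrower point stands: no DSMB time limit is stated for stillbirth.

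**The evidence of harm is mixed.** Section 3 reports more SGA with weight loss or inadequate gain, but during pregnancy. Section 2.1 cites a cohort in which weight loss between pregnancies was not associated with SGA. No likely harm is claimed here.

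**Section 2.2 as a whole is not contradicted.** Its opening sentence agrees with 6.10, and its dehydration sentence describes a conditional hazard with mitigation. The clear conflict is between 6.10 and 8.1.

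**Conclusion.** The point holds as a gap in the written plan with a cheap remedy. The only two safety endpoints in 8.1 are assigned to one arm, and 8.2 gives no comparison with controls. With no background rate, the illustrative 7 of 50 carries a tail probability anywhere from 1% to 64%. By-arm reporting makes the count interpretable, but only descriptively.

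This rests on 50 births per arm (section 8.2), on assumed background rates of 5% to 15% (5% to 10% for the power figures), and on the charter not being available. If the charter already requires by-arm tables, the change merely aligns the protocol with it.

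The stillbirth clause is secondary: expectedness is one of several conditions, and the gap is the missing DSMB time limit. The sentence in 6.10 is a wording correction.

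**What to change.** 1. **Section 8.1:** replace the reference to the intervention group with both arms. In each closed DSMB report and in the final report, tabulate SGA (below the 10th centile, one named reference), preterm delivery (before 37 weeks) and stillbirth by arm, with the risk difference and 95% CI, labelled as descriptive monitoring. Use coded arm labels so that the analysing statistician stays blinded, as 8.5 intends.
2. **Section 7.1:** add that any stillbirth, in either arm, is notified promptly to the DSMB whatever its expectedness or relatedness, and state the time limit. The existing 10-working-day limit runs to the IRB and does not serve as a DSMB limit unless the text says so.
3. **Section 6.10:** replace the no-risk statement with one that the risk to the fetus is not greater than minimal, naming the theoretical SGA and preterm risk and severe dehydration. Align the opening sentence in 2.2.

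Cost: an amendment, one extra table per report from data already collected, and a few more notifications. Regimen, visits and sample size are unchanged.

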#### 8.2 Statistical Analysis

• Describe the statistical analyses that will be performed for this study **Statistical Analysis** 

The primary analyses of Specific Aim 1a will be intent-to-treat comparisons of the LIPP and Control groups in regard to changes in maternal insulin sensitivity, BMI, and fat mass. The comparisons will be performed first with two-sample t-tests at  $\alpha$ =0.05. Should any imbalance of confounding factors in the groups be recognized, linear regression models that include significant differences (e.g. GDM) would be used to perform covariate adjustments. Based on our 1-year postpartum follow-up studies (62,63), we will have 90% power to detect an absolute or covariate-adjusted improvement in insulin sensitivity of 30% and an 80% power to detect an improvement as small as 25% in the LIPP vs. Control group. Corresponding 95% confidence intervals (95% CI) for the absolute or covariate-adjusted differences or percent improvements in insulin sensitivity between groups will be reported. We estimate the standard deviation (SD) of change in BMI from randomization until subsequent pregnancy to be 5.1 kg/m2. We will have 90% power to detect an absolute or covariate-adjusted difference in BMI of 2.6 kg/m2 and 80% power to detect a difference of 2.26 kg/m2 and 90% power to detect an absolute or covariate-adjusted difference in fat mass of 5.9 kg and 80% power to detect a difference of 5.1 kg between groups prior to the second pregnancy. The primary analysis for Specific Aim 1b is an intent-to-treat comparison of LIPP versus Control neonates with respect to fat mass at birth. The comparison will be performed using a two-sample t-test at  $\alpha$ =0.05. Linear regression will be performed, which will include weight (body composition measures) of the subject's index child as a covariate. Should any imbalance of confounding factors (for example gestational age) in the groups be recognized, linear regression models will be used to perform a covariate adjustment. Based on our preliminary data, we estimate the SD of neonatal fat mass between the LIPP and Control groups to be no more than 225 g. With at least 50 women in each group, (assuming a 50%) dropout), the t-test or linear regression will have 90% power to detect an absolute or

covariate-adjusted difference of 146 g fat mass between groups. We have 80% power to detect an absolute or covariate-adjusted difference as small as 126 g fat mass between groups. Corresponding 95% CI for the absolute or covariate-adjusted difference in neonatal fat mass between groups will be reported. For secondary analyses, we will be using the same

statistical approach. Based on our preliminary data, we estimate the SD of birth weight to be 700 g; with 50 neonates in each group we will have 90% power to detect an absolute or covariate-adjusted difference of 455 g in birth weight and 80% power to detect a 393g difference between groups. Additional secondary analyses will include umbilical cord cytokines. Comparisons will be performed using a two-sample t-test at a significance level of  $\alpha$ =0.05; however, Mann-Whitney U tests or log transformations will be employed if data are not normally distributed. Linear regression models, including confounding factors, will be used to perform covariate adjustments. Based on our published data (80), we estimate the standard deviations of umbilical cord IL-6 and CRP to be 3.4 pg/ml and 7,900 ng/ml, respectively. With 50 women in each group, we will have 90% power to detect an improvement in IL-6 and CRP levels of 50% and 42%, and 80% power to detect an improvement of 42% and 36%, respectively.

The primary goal of Aim 2 is to determine the effect of lifestyle intervention prior to pregnancy on placental mitochondrial fatty acid oxidation at term. We hypothesize that placental  $\beta$ -oxidation will be higher in the LIPP group. We will conduct an intent-to-treat analysis using two sample t-test or non-parametric Wilcoxon rank-sum test to assess differences between groups. Regression analysis will be used to assess the association of placental  $\beta$ -oxidation and enzyme activity with maternal inflammatory cytokine levels and insulin resistance in early pregnancy, along with neonatal fat mass with adjustment for gestational age and gender. Descriptive statistics, such as mean, median and range will be calculated for all variables. Power and sample size analysis based on our preliminary mitochondrial  $\beta$ -oxidation data in obese women (38±14 nmol/mg/hr) showed that a sample size of N=18/group achieves 80% power to detect a difference of 25% between groups using a two-sample t-test with a significance level of 0.05.

• *Provide a power analysis.* These are included in the statistical analyses.

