# 5 Study Design

# 5.1 Study Timelines

- Describe the duration of an individual subject's participation in the study.
  - The time that the subject will be in the study is variable. The minimum time is 13 months (4 months in study and 9 months of pregnancy). The maximum time is 28+ months. The pre-pregnancy component of the study is variable. We list 18 months in study/21 months post-partum but if the subject becomes pregnant after 21 months post-partum, she will be followed in the pregnancy component. Hence, we list 28+ months.
- Describe the duration anticipated to enroll all study subjects at the Tufts study site. Subjects will have their initial testing and randomization 3 calendar months (+/- 3 full weeks) after their delivery. Enrollment begins when the Informed Consent is signed.
- Describe the estimated date for investigators to complete this study (complete primary analyses). The initial grant ended on 11/30/2022 and we are on an approved no-cost extension until 11/30/2023.
- Describe the study procedures that will be accomplished at each study visit. At the HNRCA, CTRC or BWH Research Facility, the following metabolic testing/procedures will be performed:

Metabolic evaluations will be performed at baseline (3 months  $\pm$  3 full weeks postpartum). Follow-up evaluations will be performed after 6 ( $\pm$  3 full weeks) and 9 months ( $\pm$  3 full weeks), 15 ( $\pm$  3 full weeks) and 21 months ( $\pm$  3 full weeks) prior to pregnancy (Figure at the top of the protocol form) up to a maximum of 18 months. Once a subject becomes pregnant and has dating and viability confirmed by ultrasound, metabolic evaluations will continue at 12-16 and 32-36 weeks of gestation. However, if an individual participant has scheduling issues or there are extenuating circumstances with scheduling visits, we may schedule outside of the above windows.

Maternal Body Composition: Anthropometry measurements will include height, weight, and hip and waist circumferences. Total body fat will be measured by whole body plethysmography (Bod Pod; Cosmed, Rome, Italy), (70). We will use a hydration constant of 76% for fat free mass during late pregnancy (71). If a BodPod is not available we will use skin calipers to take skinfold measurements of the triceps and mid-axillary skinfold to estimate body fat.

Resting Energy Expenditure: Resting Metabolic Rate (RMR) will be determined after an overnight fast using the Cosmed OMNIA metabolic cart (Cosmed, Rome Italy) with a

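### Aim 1a tests change scores by unadjusted t-test and adds covariates only if they differ significantly, instead of fixing each outcome's 3-month baseline as a covariate in advance

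*Combined protocol and SAP*

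**What the plan says.** Section 8.2 sets the Aim 1a analysis as an intent-to-treat comparison of the arms "in regard to changes in maternal insulin sensitivity, BMI, and fat mass". It continues: "The comparisons will be performed first with two-sample t-tests". Adjustment is conditional: "Should any imbalance of confounding factors in the groups be recognized, linear regression models that include significant differences (e.g. GDM) would be used". No sentence names an outcome's own baseline value as a covariate. For Aim 1b, by contrast, the same section names a covariate in advance (the index child's weight or body composition).

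The baseline data exist. Section 5.1 states "Metabolic evaluations will be performed at baseline", at 3 months postpartum, and its schedules mark the OGTT and body composition at that visit for both arms. Section 2.2 places the visit before randomisation. Section 8.5 stratifies randomisation by overweight versus obese and by breastfeeding status, but section 8.2 does not carry these factors into the model.

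BMI is the only Aim 1a outcome with a stated spread: "We estimate the standard deviation (SD) of change in BMI from randomization until subsequent pregnancy to be 5.1 kg/m2". From this the section derives detectable BMI differences of 2.6 (at 90% power) and 2.26 (at 80%). For insulin sensitivity and fat mass it gives detectable differences but no SD. Section 8.1 lists the maternal measures as secondary outcomes and mentions both absolute and percent changes.

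**The concern.** A change score uses the baseline by subtracting it whole, which sets its regression coefficient at 1. If the true slope of follow-up on baseline is below 1, subtraction over-corrects. The arm that happens to start higher then appears to fall more, and baseline variation that could have been explained stays in the error term. ANCOVA estimates the slope from the same data. Apart from the degrees of freedom it uses, it is at least as precise in large samples.

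The planned safeguard does not address this. Covariates enter because they differ significantly between arms, so an imbalance too small to be significant leaves the model unadjusted while still moving the change-score estimate. The final model also cannot be known until the data are seen. At stake are some precision in the maternal results and a fully prespecified estimate. With 40 to 50% dropout expected (section 8.3), precision that needs no extra recruitment is worth having.

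**Working it through.** **Inputs.** From section 8.2: SD of BMI change 5.1 kg/m2; differences of 2.6 (90% power) and 2.26 (80%); alpha 0.05, taken as two-sided. From section 4.1: entry BMI 25 to 35 kg/m2 (23 to 32.5 for Asian populations). Not in the documents: the baseline SD at 3 months, the slope b of follow-up on baseline, and any correlation. These are assumed below and shown as ranges.

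**1. The plan's own figures.** Power = Φ(d / (SD·√(2/n)) − 1.96). No n is stated for Aim 1a. At 80 per arm the standard error is 5.1 × √(2/80) = 0.806.
- 2.6 / 0.806 − 1.96 = 1.26, so power is 89.7%.
- 2.26 / 0.806 − 1.96 = 0.84, so power is 80.0%.

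Both figures fit about 80 per arm. They do not fit the 50 per arm stated for Aim 1b, which gives 72.2% and 60.1%. The unstated n is a separate matter; 80 is used here because it reproduces the plan.

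**2. Precision gain for BMI.** The residual variance after adjustment is 5.1² − (1 − b)² × SD_baseline². A uniform spread over 25 to 35 has SD 10/√12 ≈ 2.9. Women at 3 months postpartum may spread more widely than at entry, so SD 4 is shown too. Starting from 80% power, the new power is Φ(2.802/√ratio − 1.96).

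| Baseline SD (assumed) | Slope b (assumed) | Variance ratio | Power |
|---|---|---|---|
| 2.9 | 0.5 | 0.919 | 83% |
| 2.9 | 0.7 | 0.971 | 81% |
| 2.9 | 0.9 | 0.997 | 80% |
| 4 | 0.5 | 0.846 | 86% |
| 4 | 0.7 | 0.945 | 82% |
| 4 | 0.9 | 0.994 | 80% |

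For example, 26.01 − 0.25 × 8.41 = 23.91, and 23.91/26.01 = 0.919. At b = 1 the two methods coincide.

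**3. Shift from a chance imbalance.** At 80 per arm, under simple randomisation, one standard error of the baseline difference is √(2/80) = 0.158 SD, or 0.158 × 2.9 = 0.46 kg/m2. The change-score estimate moves by (1 − b) times that: 0.23 at b = 0.5, 0.14 at b = 0.7 and 0.05 at b = 0.9. The standard error of the estimate is 0.81.

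**4. Bias check.** In 10,000 simulated trials of 80 per arm with a true effect of −2.6, the change score averaged −2.60 and −2.61 at correlations 0.5 and 0.8. ANCOVA averaged −2.60 at both. Among trials where the treated arm started more than one standard error higher, the change score averaged −3.23 and −2.99, and ANCOVA −2.61 and −2.60. The simulation assumed equal variances at the two times, hence baseline SDs of 5.1 and 8.06. It shows the mechanism and direction, but its size does not carry over to BMI here.

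**5. Insulin sensitivity and fat mass.** Without an SD or correlation, no gain can be computed for either.

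**The case against.** The strongest defence is that nothing here is invalid. The arms are randomised, baseline enters by subtraction, and the conditional regression could include it. A shift of 0.05 to 0.23 kg/m2 lies well inside sampling error that the confidence interval already covers. Stratifying by overweight versus obese also limits imbalance in BMI, and probably in fat mass. All of this stands. What remains is that the conditional rule does not name the outcome's baseline and depends on a significance test, and that stratification does not act directly on insulin sensitivity.

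Three stronger readings are tempting, and the documents do not support them.

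- **Regression-to-the-mean bias.** A reader might infer that the planned comparison is biased. Step 4 shows that it is not, averaged over randomisations. The error arises only given a chance imbalance.
- **A large power gain.** With equal variances at both times, the ratio of ANCOVA to change-score variance is (1 + ρ)/2, which takes 80% to 90% at ρ = 0.5 and 86% at ρ = 0.7. With an SD of change of 5.1, that requires a baseline BMI SD of 5.1/√(2(1 − ρ)): 5.1 at ρ = 0.5, 6.6 at 0.7 and 11.4 at 0.9. A 10-unit entry range cannot have an SD above 5. Some extra spread by 3 months postpartum is possible, but not that much at the higher correlations.
- **A remedy for dropout.** ANCOVA among women with follow-up can account for dropout related to arm and to the adjusted baseline, if the linear model holds. It does not repair dropout that depends on unmeasured factors.

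**Conclusion.** The point holds as one of efficiency and prespecification. The Aim 1a test is unbiased under randomisation. It generally gives up some precision, leaves the estimate open to chance baseline imbalance, and relies on a data-dependent rule for covariates.

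For BMI the gain is probably small: about 0 to 3 points from 80% power, given a baseline SD near 2.9 and a slope between 0.5 and 1. It reaches about 6 points only at the wider SD of 4 with a slope of 0.5. For insulin sensitivity and fat mass the size is unknown.

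Section 8.2 calls these the primary analyses of Aim 1a, but section 8.1 makes them secondary outcomes of the trial. A reader should not infer any threat to the neonatal primary comparison. The change is worth making because it costs almost nothing, not because the planned analysis would mislead.

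**What to change.** In section 8.2, replace the Aim 1a t-test with a linear model, fixed in advance, of each follow-up value on:
- randomised arm;
- the 3-month baseline of that same outcome;
- the two stratification factors (overweight/obese and breastfeeding status).

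Report the adjusted difference with its 95% CI. Where a percent improvement is to be reported, as for insulin sensitivity, fit the model on the log scale and back-transform to a ratio.

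Delete the rule under which "linear regression models that include significant differences (e.g. GDM) would be used to perform covariate adjustments". If GDM or another factor is thought prognostic, name it now, whether or not it turns out balanced. Keep the unadjusted t-test on change as a sensitivity analysis.

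The cost is a few sentences and a few degrees of freedom: one for baseline and one for each two-level factor. The data are already scheduled in both arms.
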